- Clinical Laboratory assessments include: glutamate pyruvate transaminase (GPT / ALAT), glutamicoxaloacetic transaminase (GOT / ASAT), gamma-glutamyl transferase (gamma-GT), alkaline phosphatase, total bilirubin, creatinine, chloride, potassium, sodium, total protein, albumin, Lactate, Renal function: (Creatinine, Urea and Na, K, Cl), Clotting screen including Prothrombin time, Bone profile (ca2+), High-sensitivity troponin, Ferritin, LDH, Creatinine
- 3. CRP, PCT and D-Dimer are measured in the clinical laboratory sample
- Full Blood Count: leukocytes, erythrocytes, haemoglobin, haematocrit, mean corpuscular volume (MCV), mean corpuscular haemoglobin (MCH), platelets, neutrophils, eosinophils, basophils, lymphocytes, monocytes
- 5. Pharmacodynamics: may include but is not limited to Cell-free DNA (cfDNA), Circulating histone, Citrullinated H3, NET Elisa assay
- Biomarkers: may include but is not limited to Circulating pro-inflammatory cytokines (e.g. IL-6, TNFα, IL-1β, IL-8), Markers of activation of the coagulation (e.g. fibrin, tissue factor, Von Willebrand factor,

thrombin, thromboxane A2) and complement cascade (e.g. C1q), haemolysis (e.g. red blood cell lysis), NET formation

- 7. Bronchial secretions will be collected as appropriate for clinical reasons only (e.g. spontaneous expectorant or bronchoscopy during MV)
- 8. Dornase alfa administered daily at 2.5mg BID by nebuliser
- 9. In participants who are discharged prior to Day35, a follow-up telephone call will take place to ask about their breathing.
- 10. In participants who receive dornase alfa (2.5mg BID) beyond Day7, additional blood draws and procedures will take place on Day9, Day11, Day14
- 11. Final study visit is at discharge or Day35 whichever comes first
- 12. Adverse events will be recorded every day and not just on study visit days

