#### Figure 1: COVASE Trial Schematic

Participants will be screened, consented, enrolled and randomised up to 3 days after they are admitted to the hospital. They will be randomised in a 3:1 ratio to receive BAC + dornase alfa or BAC alone. A total of 40 participants will be enrolled (30 to receive BAC plus dornase alfa and 10 to receive BAC). On Day1 to Day7 of the trial, participants randomised to the active arm, will receive 2.5mg BID nebulised dornase alfa in addition to BAC. On Day1, Day3, Day5 and Day7, blood samples will be drawn in both trial arms in order to test pharmacodynamic endpoints (PD), biomarkers and clin labs. Clinical assessments will be undertaken daily (as per UCLH clinical guidelines). Participants will be followed until discharge or death or a maximum of 28 days follow-up.

A sample size re-estimation is planned when 12 randomised participants have completed Day7 of follow-up. This analysis will ensure that the assumptions made in the sample size calculation remain valid. However, if the variability is higher than expected then up to an additional 10 participants will be enrolled and treated with dornase alfa (up to 48 participants in total).

CRP has been chosen as the Primary Endpoint because it is a clinically important marker of inflammation and is used to make clinical treatment decisions. In addition, it is induced by the overexuberant inflammation mediated by the NETs and inflammatory histones. CRP is a prognostic marker and correlates with clinical symptoms, inflammation and response to therapy.

Based on clinical judgement, it may be decided to keep some participants on treatment for up to 14 days. In particular, if participants have significant benefits from therapy, but show relapses of the COVID-19 inflammatory state (rising CRP and increasing oxygen requirements in the absence of bacterial infection), on completing 7 days of treatment, then the medical team have the choice of

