### 4. PLANNED ANALYSES

There are two planned analyses, an interim analysis after 12 randomised individuals have completed Day7 follow-up and the final analysis, once all randomised individuals have completed follow-up (which is the minimum of discharge, death or 35 days after randomisation). At the interim analysis, only the primary endpoint and safety data will be examined, and no secondary or exploratory endpoints. A promising zones approach [1] (see Section 12 for details) will be followed at the interim analysis stage to identify the conditional power and make a decision as to whether to continue enrolment up to the planned 40 individuals randomised, or whether to increase the planned sample size up to a maximum of 48 randomised individuals. See Section 12 for details.

After the final randomised participant has completed follow-up, a more complete analysis will be undertaken, including examination of endpoints relating to the primary, secondary and exploratory objectives. A full safety analysis will also be carried out at this stage.

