For the following secondary endpoints, a survival analysis will be conducted. The number of events by arm will be compared. The time to event data will be censored at 28 days post last dose (Day35) for the randomised participants and at 35 days after baseline, or the date of the last electronic record, whichever is earlier, for the historical control group. If median time-to-event times exist, the Kaplan-Meier method will be used to estimate the median time-to-event times and the associated 95% confidence intervals. The survival model will include treatment as a stratification variable and significance assessed using a log-rank test. A Cox proportional hazards model will be used to generate a hazard ratio and associated confidence intervals, adjusting for age, baseline CRP value (defined as the last CRP measurement prior to randomisation, or the first CRP following Dexamethasone for HCs) and treatment as a main effect. For the time to discharge from hospital analysis, data will be censored if the participant dies prior to discharge at the date of death.

- Survival at Day35
- Time to discharge from hospital from baseline (days) to Day 35

For the following secondary endpoint, a logistic regression model will be fitted, with age, gender, BMI baseline CRP value (defined as the last CRP measurement prior to randomisation, or the first CRP

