## **Exploristics Limited**

# Identifier: EXP20012

Clinical Study Identifier: 132333 following Dexamethasone for HCs), whether they have a key comorbidity, defined as one or more of

hypertension, diabetes or cardiovascular disease as covariates and treatment included as covariates.

- Proportion of individuals on Mechanical Ventilation (MV) over 7 days follow-up
- Proportion of individuals on Mechanical Ventilation (MV) over 35 days follow-up
- Proportion of individuals with Pneumonia over 7 days follow-up
- Proportion of individuals with Pneumonia over 35 days follow-up

For the following secondary endpoints, a linear regression model will be fitted, with age, gender, BMI, baseline CRP (defined as the last CRP measurement prior to randomisation, or the first CRP following Dexamethasone for HCs), whether they have a key comorbidity, defined as one or more of hypertension, diabetes or cardiovascular disease as covariates and treatment included as covariates.

In addition, a supplementary analysis will be fitted for the length of ICU stay, a logistic regression model will be fitted, with a 1 for the outcome if the individual had any hours in the ICU and a 0 if the individuals had no hours in the ICU, with age, gender, BMI, baseline CRP (defined as the last CRP measurement prior to randomisation, or the first CRP following Dexamethasone for HCs), whether they have a key comorbidity, defined as one or more of hypertension, diabetes or cardiovascular disease as covariates and treatment included as covariates.

- Length of ICU stay (hours) over 7 days follow-up
- Length of ICU stay (hours) over 35 days follow-up
- Time on Oxygen over 7 days follow-up
- Time on Oxygen over 35 days follow-up
- Length of hospitalisation from baseline (days)

For the "time on Oxygen" analyses, regardless of the amount of oxygen received, if there is evidence that any oxygen was provided to the participant on that day, 24 hours will be added to the time on Oxygen.

For the following secondary endpoints, descriptive summary statistics only will be presented:

- Blood pressure over 7 days follow-up
- Pulse rate over 7 days follow-up
- Temperature over 7 days follow-up
- Respiratory rate over 7 days follow-up
- Time on MV over 7 days follow-up. This will only include individuals who were on MV at any point over 7 days follow-up.
- Time on MV over 35 days follow-up. This will only include individuals who were on MV at any point over 35 days follow-up.

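### Length of hospitalisation has no common time limit, so its linear regression can favour dornase alfa if only randomised stays are cut at Day 35

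*SAP*

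**What the plan says.** The endpoint appears in SAP 2.2.2 and again in SAP 11.2 as "Length of hospitalisation from baseline (days", with no limit in either place. The other durations in the same lists have one, for example "Length of ICU stay (hours) over 35 days follow-up". The model is ordinary regression: "For the following secondary endpoints, a linear regression model will be fitted, with age, gender, BMI, baseline CRP" and key comorbidity, plus treatment. No rule covers a patient still in hospital when follow-up ends.

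For randomised patients, SAP 4 defines completed follow-up as "which is the minimum of discharge, death or 35 days after randomisation". Protocol Appendix 1, note 11, agrees: "Final study visit is at discharge or Day35 whichever comes first". SAP 3 and Protocol 5.1 give another figure: "Participants will be followed until discharge or death or a maximum of 28 days follow-up".

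For historical controls, SAP 11.2 ends observation "at 35 days after baseline, or the date of the last electronic record, whichever is earlier, for the historical control group". That sentence covers only the survival analyses, one of which is "Time to discharge from hospital from baseline (days) to Day 35". The secondary analyses use the primary analysis population, which pools randomised BAC patients with matched historical controls.

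**The concern.** The same outcome is analysed twice. The time-to-event version has a common Day 35 horizon. The version in raw days has no stated horizon. Its two main data sources differ in kind: trial patients are followed on a schedule that ends by Day 35, whereas historical controls come from a routine hospital database.

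If a long stay counts in full for a historical control but as about 35 days for a trial patient, the upper tail is removed from the whole dornase alfa arm and from only 10 of the 70 comparators. The regression then shows a shorter stay on dornase alfa with no true difference. This does not depend on how deaths are scored. Because the trial is not powered for secondary endpoints, readers will look at the estimate and its interval, and days in hospital is a figure that is easily quoted.

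**Working it through.** **Inputs from the documents.** SAP 12 plans 30 dornase alfa, 10 randomised BAC and 60 historical controls. The plan states no figure for length of stay. Its one sample-size figure (90 patients, for CRP) reproduces, with 80.7% power at 30 v 60 in a two-sided t-test, but has no bearing here.

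**Limits side by side.**

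| Analysis | Randomised patients | Historical controls |
|---|---|---|
| Time to discharge (SAP 11.2) | Day 35 | 35 days or last record, if earlier |
| ICU, oxygen and ventilation time (SAP 2.2.2) | 7 or 35 days | 7 or 35 days |
| Length of hospitalisation (SAP 2.2.2, 11.2) | none stated; follow-up ends by Day 35 | none stated |

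**Bias with no treatment effect.** Let S be the stay, with the same distribution in every group; q the share staying beyond Day 35; and e their mean number of days beyond it. Suppose randomised stays are cut at 35 and historical stays are not.

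- Dornase alfa mean: E[min(S,35)]
- Comparator mean: (10·E[min(S,35)] + 60·E[S])/70
- Difference: −(60/70)·q·e

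Neither q nor e is in the documents. With e from 7 to 30 days:

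- q = 1%: −0.06 to −0.26 days
- q = 5%: 0.857 × 0.05 × 7 = 0.30 and 0.857 × 0.05 × 30 = 1.29, so −0.3 to −1.3 days
- q = 10%: −0.6 to −2.6 days

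**Log-normal version (assumed).** Median m is 6, 8 or 10 days, with σ = ln(35/m)/z(1−q). Take m = 8 and q = 5%, so σ = 1.476/1.645 = 0.90. With stays above 120 days set to 120, E[S] = 11.91 and E[min(S,35)] = 10.99. The gap is 0.92 and the bias 0.92 × 60/70 = 0.79 days.

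**Standard error.** Let V and Vc be the variances of uncut and cut stays. Compare √[Vc/30 + (60V + 10Vc)/70²] with √[Vc(1/30 + 1/70)]. In the same example V = 161.2 and Vc = 81.4, giving 2.20 against 1.97, a rise of about 12%.

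Ranges over the three medians. Each spans two treatments of stays above 120 days: set to 120, or excluded.

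| Share beyond Day 35 | False benefit, days | Rise in standard error |
|---|---|---|
| 2% | about 0.2 | 3–6% |
| 5% | 0.6–1.0 | 8–16% |
| 10% | 1.6–2.8 | 17–32% |

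At 10% the treatment of the far tail matters: 2.0–2.8 days if long stays are set to 120, and 1.6–1.8 if they are excluded.

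**False positives.** These come from 20,000 simulated trials per setting with 30, 10 and 60 patients, medians of 7 or 10 days, stays limited to 180 days, and an unadjusted t-test. With randomised stays cut at Day 35 and 1% to 10% staying longer, two-sided rejection was 2.3–4.6% on raw days and 4.5–5.2% on the log scale. With all groups cut at 35 days (median 8; 5% and 10% beyond), the mean difference was 0.0 days and rejection was 5.0–5.2% on raw days.

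**The case against.** A reader might infer that historical stays do run to their real end, that trial stays do stop at 35 days, and that the result is therefore biased. The documents do not support that.

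- No section says an ongoing trial stay is scored as 35 days. Protocol 8.4.1 lists hospital stay among items noted as they arise. All patients are at one hospital, participants consent to access to their notes (Protocol 14), and SAP 2.2.2 already uses the hospital's EPIC database for mortality in both groups. Later discharge dates could come from there.
- No section says control stays are complete. SAP 11.2 allows a control's electronic record to end before Day 35.

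The consequence is also limited. This is one of 26 listed secondary endpoints, described as unpowered and mainly descriptive. The time-to-discharge analysis of the same outcome is free of the problem. SAP 9.2 and 11.2 allow transformation, and in the simulations the log scale reduced the distortion to a ratio of about 0.985 to 0.987 at 5% beyond Day 35 and 0.950 to 0.963 at 10%.

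Most of this stands, and it makes the bias conditional. It does not supply the missing limit. Protocol 11.1.2 treats hospital stay as obtained when the assessment period closes, and Protocol 8.4.1 places the follow-up assessment at discharge or Day 35. EPIC is named as a shared source for mortality only. Protocol 11.3.3 censors controls at their last record, whereas the SAP adds a 35-day limit. That addition matters only if some control records run past Day 35, and the SAP does not extend it to the raw-days regression.

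**Conclusion.** The point holds in conditional form. Confidence is high that the common limit is missing and moderate that bias would follow.

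If randomised stays are cut at Day 35 and historical stays are not, the linear regression favours dornase alfa under no effect by the amounts in the second table, with a wider standard error. Those figures rest on assumed log-normal stays with medians of 6 to 10 days and a 120-day limit. They also assume identical stays in all groups, because the documents give no distribution.

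The bias is zero if nobody stays beyond Day 35, if both groups use full hospital-record discharge dates, or if all groups are limited alike. A reader might also expect more spurious significance. With a Day 35 cut the simulations show none, so the harm is a biased estimate with a less precise interval. The primary endpoint and the time-to-discharge analysis are unaffected. The correction is still worth making because it costs almost nothing.

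**What to change.** In SAP 2.2.2 and 11.2:

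1. Rename the endpoint *Length of hospitalisation from baseline to Day 35 (days)*.
2. Set any longer stay to 35 days in all three sources: dornase alfa, randomised BAC and historical controls.
3. Take discharge dates from the same hospital record in every group.
4. Report the number still in hospital at Day 35 by group.

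Also reconcile the 28-day maximum in Protocol 5.1 and SAP 3 with the Day 35 end of follow-up in SAP 4 and Protocol Appendix 1. Protocol 11.3.3 and SAP 11.2 equate Day 35 with 28 days after the last dose, which may be the intended meaning, but the 28-day sentence does not say so.

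The cost is a sentence or two in the SAP and one derivation line. The downside is that days beyond Day 35 no longer count in full, in any group.

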## **Exploristics Limited**

Identifier: EXP20012

Clinical Study Identifier: 132333

The secondary outcome analysis will use the primary analysis population.

Note: if models fail to converge or have evidence of over-fitting, covariates will be removed from the models in the following order: serious condition, Sex, Age, BMI, baseline value of measurement.

### **11.3 Exploratory endpoint analyses**

Exploratory analyses will not be performed by Exploristics and will be performed separately.

#### 11.4 Safety analyses

Safety of dornase alfa will be assessed by comparisons of adverse events (AEs), serious adverse events (SAEs), treatment-emergent adverse events (TEAEs) and deaths. The safety population is defined in Section 6.4.

All AEs will be summarized by BAC + dornase alfa/BAC only. A TEAE is an AE that starts or worsens at any time after initiation of study drug on Day1 through to end of follow-up.

For SAEs occurring in  $\geq$ 5% of individuals, follow-up-adjusted event rates based on events by randomised arm will be provided. The rates will be calculated as the total number of events in the randomised arm divided by the total sum of days follow-up in that randomisation arm, multiplied by 365.25, to give the expected number of events per patient year.

Listings of all TEAEs and SAEs will be provided.

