9.1 Definitions

Term	Definition	
Adverse Event (AE)	Any untoward medical occurrence in a participant administered dornase alfa and which does not necessarily have a causal relationship with this treatment. Therefore, an AE can be any unfavourable or unintended change in the structure (signs), function (symptoms) or chemistry (laboratory data) in a participant to whom dornase alfa has been administered, including occurrences which are not necessarily caused by or related to that product.	
Adverse Reaction (AR)	Any untoward and unintended response in a participant to dornase alfa which is related to any dose administered to that participant. This includes medication errors, uses outside of protocol (including misuse and abuse of product)	
Serious Adverse Event (SAE), Serious Adverse Reaction (SAR) or Unexpected Serious Adverse Reaction	 misuse and abuse of product) Any adverse event, adverse reaction or unexpected adverse reaction, respectively, that: results in death, is life-threatening*, requires prolongation of existing hospitalisation**, results in persistent or significant disability or incapacity, or consists of a congenital anomaly or birth defect 	

	* A life-threatening event, this refers to an event in which the participant was at risk of death at the time of the event; it does not refer to an event which hypothetically might have caused death if it were more severe.
	** Hospitalisation is defined as an in-patient admission, regardless of length of stay. Hospitalisation for pre-existing conditions, including elective procedures do not constitute an SAE.
	Some medical events may jeopardise the subject or may require an intervention to prevent one of the above characteristics/consequences. Such important medical events should also be considered as serious.
	The term " severe " is often used to describe the intensity of an event or reaction (e.g. mild, moderate or severe) and should not be confused or interchanged with the term " serious ".
Suspected Unexpected Serious Adverse Reaction (SUSAR)	A serious adverse reaction, the nature, severity or outcome of which is not consistent with the Reference Safety Information.

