11.3 Statistical analysis plan

11.3.1 Summary of baseline data and flow of participants

All subjects enrolled in the study will be accounted for in a CONSORT diagram. There will be multiple analysis populations:

1 Primary analysis population - all evaluable patients randomised to dornase alfa + matched historical comparators.

2 Per protocol population - as above but excluding protocol violations.

3 Safety population - all enrolled patients receiving at least one dose of dornase alfa and the comparator groups.

4 Comparator population - the matched historical controls, patients randomised to BAC and historical records linked to biobanked samples.

5 Exploratory analysis population - all evaluable patients randomised to dornase alfa or to BAC plus historical patient data from biobanked samples.

The primary analysis will be conducted using the primary analysis population and is based on the ITT principle. Details on subjects enrolled but not included in the analysis populations will be presented as part of the CONSORT diagram.

The key baseline data that will be used to compare the groups and the analysis populations are age, gender, BMI, baseline CRP, oxygen requirements and the number of comorbidities. In general, continuous data will be summarised using the mean, standard deviation, median, minimum and maximum and categorical data will be represented as frequency counts and percentages.

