#### 6.4 Safety population

The safety population will be all patients randomised to either BAC + dornase alfa or BAC only.

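### The AE, SAE and TEAE rules are written for patients given dornase alfa and do not fit the BAC-only arm that the safety tables compare

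*SAP*

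**What the plan says.** Protocol 9.1 defines an adverse event as "Any untoward medical occurrence in a participant administered dornase alfa and which does not necessarily have a causal relationship with this treatment". The explanatory sentence in the same entry repeats the limit to people who received the drug. The serious categories are built on that term: "Any adverse event, adverse reaction or unexpected adverse reaction, respectively, that" meets one of the listed seriousness criteria. The SAP gives no AE definition of its own.

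SAP 11.4 sets the treatment-emergent period: "A TEAE is an AE that starts or worsens at any time after initiation of study drug on Day1 through to end of follow-up". No start is given for a patient who receives no study drug.

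Protocol 9.4 records SAEs from randomisation until 24 hours after the last study dose.

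The analysis nevertheless covers both arms. SAP 6.4: "The safety population will be all patients randomised to either BAC + dornase alfa or BAC only". SAP 11.4: "Safety of dornase alfa will be assessed by comparisons of adverse events (AEs), serious adverse events (SAEs), treatment-emergent adverse events (TEAEs) and deaths", and "All AEs will be summarized by BAC + dornase alfa/BAC only". For SAEs seen in at least 5% of individuals, SAP 11.4 also gives a rate by randomised arm: events divided by total days of follow-up, times 365.25. The protocol's safety set is likewise not confined to treated patients (Protocol 11.3.1): "Safety population - all enrolled patients receiving at least one dose of dornase alfa and the comparator groups".

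The ten patients randomised to BAC receive no dornase alfa (Protocol 5.1; SAP 3).

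**The concern.** A comparison between arms needs an event definition, a start and an end that exist in both arms. Here each is tied to the drug, and one arm does not get the drug. The randomised BAC patients (10 planned, 12 at the maximum sample size) are the only concurrent safety control in the SAP. If their events are undefined or filtered out, events that occur at the same rate in both arms will show only in the dornase alfa column and can be read as toxicity. The trial is open label, so staff who follow the Protocol 9.1 wording know whose events to leave out.

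The SAE rate has a related fault. Its numerator stops shortly after the last dose, while its denominator runs over all follow-up.

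**Working it through.** The documents state no figure on this point, so there is none to reproduce. The check applies each rule to each arm and then sizes the result under stated assumptions.

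**Step 1. Rules by arm**

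| Rule | Dornase alfa arm | BAC-only arm |
|---|---|---|
| AE and SAE definition (Protocol 9.1) | Applies once dosed | Never met |
| TEAE start (SAP 11.4) | First dose on Day1 | None given |
| SAE recording start (Protocol 9.4) | Randomisation | Randomisation |
| SAE recording end (Protocol 9.4) | 24 h after last dose | None given |
| SAE rate denominator (SAP 11.4) | All follow-up days | All follow-up days |
| AE review (Protocol 8.4.1, 9.2, Appendix 1) | Scheduled; AEs daily | Scheduled; AEs daily |
| Deaths (SAP 2.2.2) | EPIC database | EPIC database |

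**Step 2. Two ways of applying the rules**

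- *Literal.* BAC AEs, SAEs and TEAEs are 0/10 (0/12 at maximum size) whatever occurs.
- *Sites record BAC events as scheduled.* The all-AE summary and the SAE counts can then contain BAC events, since neither uses the TEAE filter. The TEAE output still needs a first-dose date that BAC patients lack, so the programmer must return zero or invent a rule.

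**Step 3. SAE rate**

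SAP 4 ends follow-up at the earliest of discharge, death or 35 days after randomisation. Take a patient dosed on Days 1 to 7 and followed for the full 35 days, and assume randomisation and first dose fall on Day1. SAE recording then covers about 8 days, so 35 − 8 = 27 days enter the denominator with no SAE recording. With a constant hazard, the calculated rate is 8/35 = 0.23 of the true rate. With dosing to Day14 it is 15/35 = 0.43. A patient discharged by Day8 shows no gap. For BAC the covered days cannot be stated.

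**Step 4. Size of the contrast if BAC is fixed at zero**

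Inputs: 30 and 10 patients (SAP 3). The true proportion p with an event is assumed equal in the two arms; the documents give no incidence. The apparent risk difference is p − 0 = p, although the true difference is 0. A two-sided Fisher test on x/30 against 0/10 is used only as a yardstick. The probability of the observed table is C(30,x)/C(40,x), to which the probabilities of tables no more likely are added.

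| Assumed p | Table shown | P(table) | Two-sided p |
|---|---|---|---|
| 10% | 3/30 v 0/10 | 0.411 | 0.56 |
| 20% | 6/30 v 0/10 | 0.155 | 0.31 |
| 30% | 9/30 v 0/10 | 0.052 | 0.08 |
| 40% | 12/30 v 0/10 | 0.015 | 0.02 |
| 50% | 15/30 v 0/10 | 0.004 | 0.006 |

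If the active count varies binomially and BAC stays at zero, the test falls below 0.05 in 0.0%, 6.1%, 41.1% and 97.9% of trials at p = 10%, 20%, 30% and 50%. At 36 and 12 patients the figures are 0.2%, 16.8%, 67.5% and 99.8%. With an arm-neutral definition they are at most 2.8% and 3.6% respectively.

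**The case against.** A reader might infer that the safety tables are bound to show zero BAC events and that the definitions throw the control arm away. The documents do not support that as a certainty.

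- Protocol 9.2 has all adverse events assessed every day, and Protocol 8.4.1 and Appendix 1 schedule AE review without limiting it to one arm.
- SAE recording starts at randomisation, not at first dose.
- The protocol's safety population includes the comparator groups. Its interim analysis (Protocol 11.4) describes AEs by treatment, and the SAP plans a BAC-only column.
- Day1 exists in both arms, so a common anchor is available.
- The all-AE summary and the SAE rates use no TEAE filter.
- The table shells are in a separate file that was not available here.

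Together these suggest that BAC events were meant to be captured. That stands, and it makes this a contradiction to reconcile rather than proof of an empty column. It does not cure the TEAE output or give BAC an SAE end date. Nor does it settle which text governs if a site follows Protocol 9.1.

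Three further points stand. High incidences are not established: COVID-19-related AEs and SAEs are kept out of the CRF in both arms (Protocol 9.2, 9.4, 9.5), which removes many events expected in these inpatients. The SAP plans no formal safety test, so the p values are not predictions of a reported result. And leaving out pre-dose events is the usual meaning of treatment-emergent. It is a problem here only because the category is used to compare arms when one has no dose.

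**Conclusion.** The AE, SAE and TEAE rules do not fit the BAC-only arm, and they conflict with both the arm-neutral AE review and the planned two-arm safety comparison. That mismatch is plain on the text. How far the tables are distorted depends on practice:

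- Under literal use, all three BAC counts are zero.
- If BAC events are recorded as scheduled, the fault narrows to the TEAE output and the SAE rates.
- Deaths are sound in either case, because they come from the EPIC database for all randomised patients.

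With BAC fixed at zero, the apparent risk difference equals the whole event proportion in the dornase alfa arm. At an assumed 10% to 20% this would rarely look striking at this sample size; at 40% to 50% it would. Those figures rest on equal assumed incidence and on a test that the SAP does not plan. Confidence that the wording is defective is high; confidence that the final tables are materially distorted is moderate.

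**What to change.** 1. In Protocol 9.1, define an AE as any untoward medical occurrence in a randomised participant, in either arm. The SAE definition then follows. The adverse reaction definition can stay tied to the drug.
2. In SAP 11.4, use one arm-neutral start (randomisation or Day1) and one common end for every comparative AE, SAE and TEAE table. Events after first dose in the dornase alfa arm can be listed separately if wanted.
3. Align the SAE recording window in Protocol 9.4 and the SAE-rate denominator in SAP 11.4 with that same period in both arms, so that only days on which SAEs are recorded are counted.

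The cost is mainly wording, since AE review is already scheduled for both arms. A few pre-dose events in the dornase alfa arm will enter the comparative tables, and BAC events must be recorded over the same window. If the common end is later than 24 hours after the last dose, SAE recording also runs longer in the dornase alfa arm. If BAC events were left out of the CRF during the trial, programming cannot restore them. The medical records, where Protocol 9.2 has AEs noted first, would have to be checked.
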